Specific Aim 2: Manual function. To evaluate the effects of the training program incorporating ride-on-toys on manual abilities and spontaneous use of the affected arm in children with hemiplegic CP as measured using standardized tests and objective/kinematic measures.

- Aim 2A: We hypothesize that there will be greater improvements in affected arm active movement control and spontaneous functional use as assessed using standardized tests (Quality of Upper Extremity Skills and Shriner's Hospital Upper Extremity Evaluation) and a parent-rated questionnaire (ABILIHAND-Kids), following the intervention phase compared to the control phase. During the intervention phase, children will also show improvements in movement control and maneuverability of the ride-on-toy from an early to a late training session.
- Aim 2B: We hypothesize that children will also show improved motor control and movement kinematics during reaching in terms of increased movement speed, smoothness, straightness, and symmetry, decreased movement variability, and improvements in peak and average velocity of reaching. Children will also show greater improvements in daily arm activity measured through objective wrist-worn activity monitors during the intervention compared to the control phase.

Clinical Impact: This project, led by an early career investigator, strategically leverages the expertise of an interdisciplinary team that comprises experts from physical therapy, occupational therapy, and biomedical engineering who are well suited to implement the proposed project. Our work aligns with the strategic plan of the AACPDM in (1) embracing innovative approaches to advance knowledge and practice in the field of CP and (2) fostering research that will generate new knowledge and evidence to inform care of people with CP. The proposed research will provide evidence to support an innovative, child-friendly, low-cost, home-based training program using commercially-available ride-on-toys that can be implemented by clinicians and families to promote spontaneous, self-initiated practice using the affected UE and improved manual function in children with hemiplegic CP.

RESEARCH METHODS/PLANS

1. Study design: Single group longitudinal design. Children will be observed for a 6-week control phase (conventional treatment-as-usual) followed by a 6-week experimental phase (conventional therapy + RNT).

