1. Primary: Adherence – The toy will collect data on amount of use during training. Researchers and caregivers will also maintain logs during the intervention phase to document training duration and child engagement. 2. Primary: Treatment satisfaction and engagement - Children will complete the valid and reliable, 16-item Physical Activity Enjoyment Scale (PAES) to rate their experience.⁶⁷⁻⁶⁹ Training sessions (one early, mid, and late session each) will be video-coded for child affect (i.e., smile rates, % duration of positive/interested and negative affect) and attention (i.e., % duration of attention to task-relevant targets). Children and/or caregivers will fill out exit questionnaires to assess training satisfaction, enjoyment, repeatability, and caregiver burden. 3. Primary: Treatment fidelity – An unbiased coder will randomly code video data (one each of early, mid, and late sessions) from researcher-delivered sessions using fidelity checklists to assess adherence to the training protocol. Trainers will also fill out posttest exit questionnaires to assess ease of implementation of RNT. 4.2.1. Aim 2A: Manual abilities and spontaneous affected UE use will be assessed as follows -1. Primary: Quality of Upper Extremity Skills Test (QUEST)⁷⁰– This criterion-referenced reliable and valid test assesses UE movement quality using unimanual items scored on a dichotomous scale in 4 domains: grasp, dissociated movement, protective extension, and weight bearing. The scale is valid up to 12 years of age.⁷¹ 2. Primary: Shriner's Hospital Upper Extremity Evaluation (SHUEE)⁷²– This video-based valid and reliable test assesses affected UE use spontaneously and on tester demand in 16 bimanual tasks in 3-18-vear-old children. It has 3 parts: spontaneous functional analysis, dynamic positional analysis, and grasp-release analysis. 5. Secondary: Navigation control and accuracy – Early & late training sessions will be coded for (1) % duration of assisted (child needs trainer-provided manual assistance) versus independent navigation, (2) average duration and number/session of child-initiated, movement bouts normalized by driving time (a bout comprises 1 acceleration and 1 deceleration phase), and (3) rates/session of path deviations and obstacle bumps. 4. Secondary: ABILHAND-Kids⁷³– This valid and reliable parent-rated questionnaire rates the child's difficulty level (3-point ordinal scale of 'impossible', 'difficult', or 'easy') in performing 21 bimanual skills independently. 4.2.2. Aim 2B: 1. Primary: Kinematic measures – Data will be collected during a unilateral and bilateral reachgrasp task at self-selected speed involving different objects (foam ball, rattle, and square block) placed at half arm's length (near) and at arm's length (far) on the table. Sensors (Inertial Measurement Units (IMUs)) will be placed on both hands, both forearms, both arms, and the C7 spinous process. We will assess the speed. smoothness, variability, and symmetry of reaching trajectories. Kinematic and motion data will also be obtained during weekly researcher-delivered training sessions and through toy-mounted sensors. 2. Secondary: Arm activity – Wrist-worn Actigraph activity monitors will be worn during first and last week of

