
control and intervention phases to assess changes in daily arm activity over the course of the study. **5. Training protocol** – Children will continue to receive conventional therapy such as physical and occupational therapy throughout the study. During the first 6-week control phase, researchers will keep track of conventional therapy received (frequency, duration/session, type) on a weekly basis through parent interviews/training logs. In the second 6-week intervention period, in addition to conventional therapy, children will receive ride-on-toy navigation training (RNT). Researchers will provide 2 sessions/week and caregivers will provide 2 sessions/week each lasting 20-30 minutes. Training will occur at the child's home/school/community spaces like YMCA, playground, etc. Families without access to such spaces will have the option to visit the PI's lab for training. The toy can be driven on different surfaces, e.g., wood, grass, concrete, carpet, etc., allowing for flexibility in accommodating unique space-related constraints faced by families. During weekly visits, researchers will coach caregivers for caregiver-provided sessions. Trainer will fill out training diaries to log details of intervention delivery and child progress. Children will use only their affected arm to move the joystick and the unaffected arm will be enclosed in a soft restraint to encourage use of the affected side during RNT. Each session will include periods of "free play" (child can navigate freely through their physical environment using toy) and "structured play" (child will participate in multi-directional navigation games such as shape mazes, treasure hunts, and obstacle courses). The intervention is based on the motor learning- and familycentric practice-based training principles: variable and repetitive practice, progressive challenges tailored to child needs, activities promoting problem-solving and trial-and-error learning, immediate visual and auditory feedback, playful exploration, incorporation of child-preferred toys/themes into games to increase motivation, and involvement of caregivers and siblings during training. Training will emphasize active UE control of the joystick for starting and stopping the toy, moving steadily forward and backward, turning to the right and left, 180° and 360° turns on both sides, and avoiding obstacles. Activities will also involve small toys/props to encourage gross and fine motor movement and control of affected UE. Trainers will follow a least-to-most prompting hierarchy involving gestural, verbal, and finally hand-on-hand assistance per the child's needs during training. **6.** Project timeline – Please see detailed study timeline below.

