
Proposed study activities	Year 1	Year 2			
(Q indicates Quarter)	Oct - Dec	Jan-Mar	Apr-Jun	Jul-Sep	Oct-Dec
Intervention development and IRB Approval					
Ride-on-toy modifications and retrofitting					
Recruitment					
Testing/training: Round 1 (5 children)					
Testing/training: Round 2 (5 children)					
Testing/training: Round 3 (5 children)					
Data analysis					
Data dissemination & preparation for R21/R34 grant					

7. Dependent variables and Statistical analyses - For all coded video data, 2 independent coders will rate 20% of the data to establish inter- and intra-rater reliability of over 90%. Standardized tests will be compared between control and intervention phases, training-specific measures will be compared between early, mid, and late training sessions. All kinematic and activity data will be post-processed using custom MATLAB programs. Dependent variables from pretest-mid-point-posttest measures include: (a) total unilateral scores from affected and unaffected sides on sub-tests of the QUEST, (b) total and % scores on sub-sections on the SHUEE, (c) bilateral range of motion, maximum joint angles, peak and average velocity, total movement time, number of movement units, movement straightness, movement variability, and smoothness (e.g. jerk, dimensionless jerk, and log dimensionless jerk)^{74,75} during kinematic tasks, and (d) raw scores on the ABILHAND-Kids and PAES questionnaires. Dependent variables for training-specific measures include: (a) rates of smiles and % duration of positive/interested versus negative affect. (b) % duration of assisted and independent mobility. (c) number and duration of movement bouts during navigation using the ride-on-toy, (d) outcomes derived from kinematic data (as listed in point (c) above) during the training-specific navigation test, and (e) activity counts collected from activity monitors. All data will be evaluated for assumptions of parametric statistics and general or generalized models will be selected accordingly. Variables that violate distributional assumptions of normality will be analyzed using generalized linear model (GLM) procedures, which enable the use of non-Gaussian error models. We anticipate limited missing data because attrition rates are typically low in home-based versus clinic-based programs.^{76,77} When applicable, missing data will be evaluated to determine if it is completely at random. If random, multiple imputation by maximum likelihood estimation will be used.⁷⁸

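### In the intervention phase only, the wrist-monitor counts for daily arm activity include training-session time, and the contrast that decides how much this matters is not defined

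*Combined protocol and SAP*

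**What the plan says.** Section 4.2.2 (Aim 2B, secondary measure, arm activity) states: "Wrist-worn Actigraph activity monitors will be worn during first and last week of" the "control and intervention phases to assess changes in daily arm activity over the course of the study". The Aim 2B hypothesis reads: "Children will also show greater improvements in daily arm activity measured through objective wrist-worn activity monitors during the intervention compared to the control phase".

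Section 5 sets the training content of each intervention week: "Researchers will provide 2 sessions/week and caregivers will provide 2 sessions/week each lasting 20-30 minutes". On arm use in those sessions it says: "Children will use only their affected arm to move the joystick and the unaffected arm will be enclosed in a soft restraint". The control phase is conventional therapy only.

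Section 7 says of processing only that "All kinematic and activity data will be post-processed using custom MATLAB programs". It lists "activity counts collected from activity monitors" under the training-specific dependent variables, not under the pretest, mid-point and posttest variables, and says that "training-specific measures will be compared between early, mid, and late training sessions".

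No section says that monitors come off during training, that session time is cut from the counts, or that in-session and out-of-session activity are separated.

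**The concern.** Aim 2 concerns spontaneous use of the affected arm, and the monitors are its sensor-based window on ordinary days. Arm use in a training session is not spontaneous: the task requires the affected arm and the other arm is restrained. If session minutes stay in the counts, intervention weeks contain a block of required affected-arm use that control weeks lack. A higher count could then come partly from delivering the treatment and be read as carry-over into daily life.

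How far this matters depends on the contrast, and the plan leaves that open. The Aim 2B hypothesis compares phases. Section 7 puts the counts in a list to be compared across early, mid and late training sessions. That does not fit a measure worn in two weeks per phase, with no mid-phase week, and worn also in a phase that has no training sessions.

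**Working it through.** The plan gives no figure for this outcome. Its one computed figure, the 82% power in section 8, does not enter here.

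**Inputs from the documents**
- Monitor weeks: first and last week of each phase (section 4.2.2).
- Sessions per intervention week: 2 + 2 = 4, of 20-30 minutes each (section 5), so t = 80 to 120 minutes per week.
- Outcome variable: activity counts (section 7).

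**Inputs assumed, because the documents do not give them**
- Wear time of 8 to 14 hours a day for 7 days, so T = 3360 to 5880 minutes per week.
- r, the affected-arm count rate in sessions divided by the rate in ordinary time: 1.5 to 4.
- Monitors stay on during sessions.
- No carry-over: the ordinary rate is the same in all weeks.

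**Control week against intervention week**

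Set the ordinary rate to 1. A control week totals T. An intervention week totals (T − t) + r·t = T + (r − 1)·t. The rise with no carry-over is therefore (r − 1) × t/T.

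| Wear, h/day | t, min | t/T | r = 1.5 | r = 2 | r = 3 | r = 4 |
|---|---|---|---|---|---|---|
| 8 | 80 | 2.38% | 1.19% | 2.38% | 4.76% | 7.14% |
| 8 | 120 | 3.57% | 1.79% | 3.57% | 7.14% | 10.71% |
| 12 | 80 | 1.59% | 0.79% | 1.59% | 3.17% | 4.76% |
| 12 | 120 | 2.38% | 1.19% | 2.38% | 4.76% | 7.14% |
| 14 | 80 | 1.36% | 0.68% | 1.36% | 2.72% | 4.08% |
| 14 | 120 | 2.04% | 1.02% | 2.04% | 4.08% | 6.12% |

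The range is 0.7% to 10.7%. The sign depends on r: if sessions produced fewer affected-arm counts per minute than ordinary play (r below 1), the error would go the other way.

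**Last minus first week within the intervention phase**

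With in-session rates r1 in the first week and r2 in the last, and the same t, the relative change with no carry-over is (r2 − r1)·(t/T) ÷ [1 + (r1 − 1)·(t/T)].
- If r1 = r2, this is 0: session time cancels.
- The Specific Aims section says that training is made harder each week. If that raised the rate from 2 to 3, the residue would be 0.0136/1.0136 = 1.3% (80 minutes, 14 h/day) to 0.0357/1.0357 = 3.4% (120 minutes, 8 h/day).
- A different number of sessions delivered in the two weeks would also leave a residue, because t would then differ.

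**After removing session windows**

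The count per unit of remaining wear is (T − t)/(T − t) = 1, the same as in a control week, so the direct session contribution is 0. The division by remaining wear time is needed: cutting the windows but keeping weekly totals would produce a false fall of t/T, or 1.4% to 3.6%.

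**The case against.** The strongest reply is that the Aim 2B wording on greater improvement, together with monitors at the start and end of each phase, most naturally means change within each phase, compared between phases. Both intervention weeks carry the same planned training, so session time mostly cancels. That stands. A reader might infer that the hypothesis could be met by treatment delivery alone. The documents support that only for a comparison of control-week with intervention-week levels, which they do not specify. Under the within-phase reading, one remaining weakness runs against the intervention: its first week is already treated, so gains made in that week are missed.

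A reader might also work with an affected-to-unaffected ratio, where the restraint lowers the denominator. With assumed activity of 30% and 40% in ordinary time, 60-100% and 0% in sessions, and wear of 8-12 hours a day, the ratio rises from 0.75 to between 0.774 and 0.843 (+3.2% to +12.3%). The plan names counts for the monitors, not a ratio, and none of those activity levels is in it. The result is also fragile. At 12 h/day and 120 minutes, the high case is 1596/1968 = 0.811 (+8.1%). If riding a moving toy registers on the restrained wrist at 50% instead of 0%, it falls to 1596/2028 = 0.787 (+4.9%).

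Two further points are fair. Continuous wear during sessions is inferred, not stated. The measure is secondary in a 15-child single-group pilot, and the QUEST, SHUEE and reach-task results are untouched. Neither point removes the missing rule or the undefined contrast.

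**Conclusion.** The point holds in limited form. The overlap and the absence of any rule to remove session time follow directly from sections 4.2.2, 5 and 7. Section 7 also does not fix the contrast, and it lists the counts under a heading that does not fit them.

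The consequence is conditional. Comparing control with intervention weeks, session time alone would move affected-arm counts by roughly 1% to 11%, given monitors left on, 8-14 h/day wear and r of 1.5 to 4. Under a last-minus-first-week change within each phase it largely cancels, leaving about 1.3% to 3.4% if weekly progression raised the in-session rate from 2 to 3 times the ordinary rate, plus anything due to unequal session delivery. What is limited is the daily-life reading of one secondary outcome. The change is worth making before the activity results are finalised, but it does not threaten the trial's main conclusions.

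**What to change.** In section 7:

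1. State that the Aim 2B activity contrast is the within-phase change (last minus first week) compared between phases, and move activity counts out of the training-specific list.
2. Define the daily-activity outcome as counts per hour of wear time outside training sessions. Cut whole session windows, not only toy driving time, because sessions also include prop activities. Do this wherever logs, diaries or toy data give clock times.
3. Report counts including session time alongside, and in-session activity separately as delivered practice.
4. Where clock times are missing, report the overlap as a limitation. If monitors are in fact taken off for training, say so.

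Do not replace the first intervention week with the last control week as the main reference. The intervention contrast would then run from week 6 to week 12 (six weeks) against week 1 to week 6 (five weeks) for control, which favours the intervention in growing children with no concurrent group. It can be shown as a supplementary comparison, which would also pick up first-week gains.

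The cost is a few sentences and a filtering step in the planned processing. It drops 80-120 minutes per intervention monitor week. Sections 3 and 4.1 promise total operating time and training duration, not start and stop times, so applying the rule to children already completed depends on whether time-stamped records exist. The continuing-review report gives data collection as complete for 12 children, 4 in progress and analysis begun. The rule should therefore be dated and described as added at that stage, with both versions of the counts shown.

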8. Power analysis – Being the first study to assess effects of ride-on-toy training on UE function in CP, we do not have prior effect size estimates for outcome measures. Therefore, our sample size estimates are derived based on large-sized effects detected in studies that aimed to improve UE function in CP using (a) innovative games such as virtual reality and video games and (b) home-based conventional therapy programs. Effect size estimates in these studies varied from 0.83-1.16 in favor of the intervention group.^{46,79,80} Considering sources (a & b) and our data collection plan, we determined sample size estimates assuming fixed-effects analysis of variance on a 1x 3 design, 1 group and three time points. The study will include a total of 15 cases. The criterion for significance (alpha) has been set at 0.05 (two-tailed). The effect size estimate is 0.80, which yields power of 82% in the most conservative scenario of the effect size estimates we found in the literature.

PROPOSED INVESTIGATORS/SITES AND CONTRIBUTIONS

[name] (PI) is a pediatric physical therapist (PT) with significant experience over the past 12 years in developing novel, creative movement interventions for children with disabilities and working as part of interdisciplinary teams of engineers, designers, and health professionals to develop assistive technologies for children. She also has expertise in designing and conducting clinical trials in patient populations specifically in children with developmental disabilities. [name] will be responsible for project supervision and coordination of the study. She will be responsible for maintaining all study activities including recruitment, data collection, data analyses, and reporting. She will work closely with the Co-Is on all aspects of the study. She will be involved in intervention development and behavioral outcome assessments. She will also leverage her professional networks and alumni connections from the Doctor of Physical Therapy program at the University of Connecticut to assist with participant recruitment. [name] will work with and oversee efforts of graduate and undergraduate students in her lab to train them on procedures related to participant screening and consent, data collection, data coding, and data analyses. She will also oversee ongoing procedures throughout the duration of the study related to ensuring fidelity of data collection and data coding methods.

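### Section 7 does not define the gain-versus-gain contrast that Aim 2A needs, and it places activity counts under a comparison that cannot test Aim 2B

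*Combined protocol and SAP*

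**What the plan says.** The design is a single group: six weeks of usual therapy, then six weeks of usual therapy plus ride-on-toy training. Assessments are at pretest (Pre), at the end of the control phase (Mid) and at the end of the intervention phase (Post).

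- **Aim 2A** expects larger improvements on QUEST, SHUEE and ABILHAND-Kids "following the intervention phase compared to the control phase".
- **Aim 2B** says that "children will also show improved motor control and movement kinematics during reaching", and separately expects "greater improvements in daily arm activity measured through objective wrist-worn activity monitors during the intervention compared to the control phase".
- **Section 4.2.2** provides the data for the second part of Aim 2B: "Wrist-worn Actigraph activity monitors will be worn during first and last week of" each of the two phases.
- **Section 7** gives the analysis as "Standardized tests will be compared between control and intervention phases". It lists the scores at the three visits as dependent variables and leaves the model to be general or generalized according to assumption checks. Activity counts appear in its list of training-specific measures, which are to be compared across early, mid and late training sessions.
- **Section 8** assumes a "fixed-effects analysis of variance on a 1x 3 design, 1 group and three time points". It adds: "The criterion for significance (alpha) has been set at 0.05 (two-tailed"), and "The effect size estimate is 0.80, which yields power of 82" percent. It does not say what the 0.80 is standardised by, and it gives no between-visit correlation.

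**The concern.** Aim 2A concerns a difference between two changes, (Post-Mid) against (Mid-Pre). No such quantity is written in section 7 or section 8. Mid closes the control phase and Post closes the intervention phase, so a plain Post-versus-Mid test satisfies the wording of section 7. An overall test of three visit means satisfies section 8. Neither separates a training effect from change that would have happened anyway.

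That matters here because the children are 3 to 8 years old, are tested three times, and have no concurrent control group. The control phase is the design's only protection against maturation and test practice, and it protects only if the two phase changes are contrasted within child.

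The activity-count problem is of a different kind. The data needed for the phase comparison are collected, but the rule in section 7 compares points that all lie inside the intervention phase.

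**Working it through.** **Inputs.** From the documents: 15 children, three visits, two-sided alpha 0.05, effect size 0.80, power 82%. Assumed, because the documents give neither: an equal correlation rho between every pair of visits (0.5, 0.8, 0.9) and a drift of g score-SDs in each phase. Scores have unit SD.

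**1. The plan's 82%.**
- Paired t-test, df 14, noncentrality 0.80 x sqrt(15) = 3.10: power **82.1%**.
- ANOVA on independent scores: f = 0.80 with 15 scores (df 2,12; noncentrality 15 x 0.64 = 9.6) gives 68%; f = 0.80 with 45 scores (df 2,42; 28.8) gives 99.8%; f = 0.40 with 45 scores (df 2,42; 45 x 0.16 = 7.2) gives 64%.
- Repeated-measures ANOVA, f = 0.40 (d = 0.80 halved), df 2,28, noncentrality 7.2/(1-rho): 62% at rho 0; **81.9%** at rho 0.36 (noncentrality 11.25); 91% at rho 0.5.

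So 82% fits one paired comparison, or a repeated-measures ANOVA at one particular correlation. It does not fit an independent-scores ANOVA.

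**2. False positives under equal drift and no training effect.** Post-Mid has mean g and SD sqrt(2(1-rho)), so dz = g/sqrt(2(1-rho)). The contrast has mean g - g = 0.

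| Drift per phase | dz at rho 0.5/0.8/0.9 | Post-versus-Mid rejects | Gain contrast rejects |
|---|---|---|---|
| 0.05 SD | 0.050/0.079/0.112 | 5/6/7% | 5% |
| 0.1 SD | 0.100/0.158/0.224 | 6.5/9/13% | 5% |
| 0.2 SD | 0.200/0.316/0.447 | 11/21/36% | 5% |

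The repeated-measures omnibus test has noncentrality 15 x 2g²/(1-rho). At g = 0.2 this is 2.4/6/12, and the test rejects 24/54/84%. By itself it shows only that visits differ. An ANOVA that ignores the pairing is at or below nominal at 0.2 SD (5/1/0.4%, simulated) and rejects 39/33/30% at 0.4 SD.

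**3. Activity counts.** Set the three places side by side. Aim 2B compares phases; section 4.2.2 collects the opening and closing week of each phase; section 7 compares training sessions, which exist only in the second phase. No assumption is needed to see that the last cannot answer the first. For scale, closing-versus-opening week of the intervention phase alone has the same dz formula as step 2: with 0.2 SD drift within each phase it rejects 11/21/36%, against 5% for the phase contrast.

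**4. Power of the gain contrast at n = 15.** Take 0.80 as the excess of the intervention gain over the control gain.
- In raw-score SDs, Post - 2 x Mid + Pre has variance 6(1-rho), so dz = 0.80/sqrt(6(1-rho)).
- In SDs of a six-week gain, with correlation r between the two gains, dz = 0.80/sqrt(2(1-r)).

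| Reading | Correlation | dz | Power | n for 80% |
|---|---|---|---|---|
| Raw SD | rho 0.5 | 0.46 | 38% | 39 |
| Raw SD | rho 0.7 | 0.60 | 58% | 25 |
| Raw SD | rho 0.8 | 0.73 | 75% | 17 |
| Raw SD | rho 0.83 | 0.79 | 81% | 15 |
| Raw SD | rho 0.9 | 1.03 | 96% | 10 |
| Gain SD | r -0.5 | 0.46 | 38% | 39 |
| Gain SD | r 0 | 0.57 | 53% | 27 |
| Gain SD | r +0.25 | 0.65 | 65% | 21 |
| Gain SD | r +0.5 | 0.80 | 82% | 15 |

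If 0.80 already standardises the difference of gains, power is 82.1%.

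**5. What the contrast does not remove.** With drift of 0.1 SD then 0.3 SD and no training effect, the contrast has mean 0.2 and gives a false favourable result in 6/10/15% (nominal 2.5% in that direction); Post-versus-Mid, with mean 0.3, gives 19/40/68%. If the first retest gain is the larger (0.3 then 0.1 SD), a true 0.8 raw-SD effect leaves a contrast of 0.6, and power falls from 38% to 24% at rho 0.5 and from 75% to 51% at rho 0.8.

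**The case against.** The strongest reply is that the plan, read as a whole, already says the right thing. Section 7 compares phases, not visits; Aim 2A speaks of improvements; three visits yield exactly two changes. The section 8 ANOVA is a sample-size assumption, not the analysis. Most of this stands. A reader might infer that the plan has chosen Post-versus-Mid, or that it will report an omnibus test as efficacy. The documents support neither: those tests are permitted, not planned. What remains is that an aim does not fix an analysis, and nothing in sections 7 or 8 rules the weaker tests out.

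A reader might also infer that the 82% is simply wrong for an ANOVA. That goes too far. The words of section 8 point to a fixed-effects model, which does not give 82%, but one group at three time points can also be read as repeated measures, and step 1 shows a version that does.

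Section 7 states no term for child, and its missing-data rule is brief. These are missing details rather than separate faults; in particular, omitting the child term loses power and does not create false efficacy.

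On activity counts, a misfiled list item is the likely explanation, and the outcome is secondary. That explains the conflict but does not resolve it.

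Finally, the drift is assumed. That is true, and it limits the size of the concern, not its logic: Aim 2A calls for gain against gain whatever the drift.

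**Conclusion.** The concern holds as under-specification of the main efficacy comparison, together with one rule that is wrong as written.

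- **Aim 2A.** The contrast is not defined. How much a Post-versus-Mid reading would matter depends on drift and correlation that the documents do not give. The excess is slight at 0.05 SD per phase. At 0.1 SD it is modest at low correlation but reaches 13% at rho 0.9. At 0.2 SD it is roughly two to seven times nominal.
- **Activity counts.** The comparison assigned in section 7 cannot test Aim 2B. This rests on the text alone.
- **Power.** The 82% is the power of the gain contrast only if 0.80 already standardises the difference of gains, or if the correlation is favourable (rho about 0.83 in raw SDs, or r = +0.5 in gain SDs). The documents do not say.

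The calculations use the planned 15 children, normal scores and equal between-visit correlation.

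**What to change.** **(a) Name the contrast.** For QUEST and SHUEE (primary) and ABILHAND-Kids (keeping its secondary status), test (Post-Mid)-(Mid-Pre) within child and report its 95% CI. Use a model with visit fixed, child random and small-sample degrees of freedom, checked against a one-sample t-test on each child's Post - 2 x Mid + Pre. Aim 2B claims only improvement in reaching kinematics, so use the same contrast there for any statement that training caused the change; otherwise report within-child change as such.

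**(b) Activity counts.** Move them out of the training-session list and analyse (last - first week, intervention) - (last - first week, control) within child.

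**(c) Power.** Restate it for the gain contrast, saying what 0.80 standardises and which correlation is assumed, and show the range in step 4. With most data already collected, the expected precision is at least as informative: the 95% half-width is t(0.975,14) x sqrt(6(1-rho)/15), with t = 2.145, which is 0.96/0.61/0.43 raw SD at rho 0.5/0.8/0.9.

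**Cost.** No new data or visits. There are three downsides. The stated power may fall. The contrast removes only change that is equal in both phases, and the plan should say so. And this is not clean pre-specification: the progress report (Section IV) records data collection finished for 12 children and analysis under way, so the text must be dated and described as written after analysis started.
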